4.3 Handling of Missing Data

All missing or partial data will be presented in the subject data listing as they are recorded on the electronic case report form (eCRF). Missing data proportions will be reported.

In general they will not be substituted or replaced, except for the parameters described below.

General rules

- **Efficacy variables**

Last visit is defined as last observed value post-baseline (including unscheduled visits, but not including follow-up), if not specified otherwise.

- **6 Minute Walking Distance**

If a subject dies before Week 24 or during follow-up after termination before Week 24, the worst value = 0 is used.

- WHO Functional Class

If a subject dies before Week 24 or during follow-up after termination before Week 24, the worst value = IV (4) is used.

- **Safety variables**

Last visit is defined as last observed value post-baseline (including unscheduled visits, but not including follow-up), if not specified otherwise.

Treatment emergent events, phases, period and relative days will be derived according to standard guidelines.

A complete date is not needed for the statistical tables, but an imputation on the phase of the study for adverse events and concomitant medications (pre, during or post) is required. The 'minimum' rule will be used for start dates which is first day of month or 1st of January. The 'maximum' rule will be used for end dates which is last day of month or 31st of December.

- **Child Health Questionnaire (SF-10)**

Scores will be provided by QualityMetric Score was generated by QualityMetric.

- **Pediatric Quality of Life Inventory™ (PedsQL™)**

In the case of missing single questionnaire items, the missing data rules in the scaling and scoring document will be followed. Specifically, if more than 50% of the items in the scale are missing, the Scale Scores should not be computed. If 50% or more items are completed: Impute the mean of the completed items in a scale.

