## 8.9 Premature discontinuation of study medication

Subjects must be withdrawn from the study for the following reasons:

- At their own request or at the request of their legally acceptable representative at any time during the study and without giving reasons, a subject may decline to participate further. The subject will not suffer any disadvantage as a result

- If, in the investigator's opinion, continuation of the study would be harmful to the subject's well-being.
- If any AE occurred which is not acceptable in the opinion of the investigator and / or participating parent(s)/legal representative(s) or subject
- Occurrence of adverse drug reactions, which have from the investigator's point of view, a negative impact on the subject's individual risk-benefit ratio.
- If treatment is interrupted for more than 3 days during any individual dose titration phase
- If treatment is interrupted for more than 14 consecutive days during the maintenance phase.
- In case a female subject of childbearing potential is not compliant with pregnancy testing
- In case of lung transplantation
- In case of pregnancy or breast feeding
- In case that the subject fulfills one of the stopping criteria specified in Section 5.1.1
- Subject does not tolerate the lowest possible riociguat dose (0.5 mg TID)
- Patient with pulmonary hypertension associated with idiopathic interstitial pneumonias (PH-IIP)

Discontinuation of bosentan or other ERA treatment (i.e. due to elevated liver enzymes) during the course of the study does not mandate withdrawal of the subject from the study. Also, discontinuation PCA treatment, during the course of the study, does not mandate withdrawal of the subject from the study. The final decision of withdrawal will be the responsibility of the investigator.

The DMC may recommend stopping the trial due to an unfavorable risk benefit assessment during the course of the trial. The final decision to terminate will be the responsibility of the Sponsor.

If the subject or parent(s)/legal representative(s) withdraw(s) consent to treatment with study drug, the investigator will ask to continue with study visits as planned, only with the aim to collect potential study outcomes and AEs. If the subject/parent(s)/legal representative(s) state to the investigator that they no longer authorize to continue to obtain outcome data, this will be respected and documented in the source records, and no further study data will be collected.

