In all subjects who prematurely discontinue study drug for other reasons than withdrawal of informed consent, study visits will take place as planned to collect potential study outcomes and AEs.

*(Note the section was modified according to Amendment 6, see Sections 17.3.1.1 and 17.3.1.2.)*

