4.2 Handling of Dropouts

A subject who discontinues study participation prematurely for any reason, as specified in the protocol in section 8.9, is defined as a “dropout” if the subject has already started treatment. Dropouts will not be replaced.

In all subjects who prematurely discontinue study drug at any time after Visit 1 and before Visit 9 for reasons other than withdrawal of informed consent, an end-of-treatment visit has to be performed. The same procedures as at Visit 9 will be performed with the exception of the X-ray of left hand.

For all subjects stopping study medication either at the end of treatment or prematurely discontinuing the study at any time, a safety follow-up visit 60 days (± 8 days) after last study medication intake should be performed.

If the subject or parent(s)/legal representative(s) withdraw(s) consent to treatment with study drug, the investigator asks to continue with study visits as planned, only with the aim to collect potential study outcomes and AEs. If the subject/parent(s)/legal representative(s) state to the investigator that they no longer authorize to continue to obtain outcome data, this is respected and documented in the source records, and no further study data are collected.

In all subjects who prematurely discontinue study drug for other reasons than withdrawal of informed consent, study visits takes place as planned to collect potential study outcomes and AEs. The analysis will be performed independently of the fact whether a patient had drug intake or not.

A subject who discontinues the study prior to the first intake of the study treatment is defined as ‘screening failure’.

The number of screening failures and dropouts as well as the respective reasons will be summarized.

The frequency of enrolled subjects not completing screening, treatment phase, safety follow-up for those not entering the long-term extension and associated reasons will be summarized.

A Kaplan-Meier plot of the time from start of study treatment to end of study treatment will be provided. Subjects continuing study treatment in the LTE phase will be censored on his/her end of main phase.

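### SAP 4.3 gives a worst value for walk distance and WHO class only on death, so measurements taken after a lung transplant count as week-24 change on riociguat

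*SAP*

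**What the plan says.** SAP 4.3 leaves missing data alone by default: "In general they will not be substituted or replaced, except for the parameters described below". Among the exceptions, only two concern a clinical event, and in both the event is death. For 6MWD: "If a subject dies before Week 24 or during follow-up after termination before Week 24, the worst value = 0 is used". For WHO functional class, in the same circumstances, "the worst value = IV (4) is used". Echocardiography, NT-proBNP/BNP and the quality-of-life scores have no event-based rule at all; PedsQL has only a rule for missing items.

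Protocol 8.9 opens its list with "Subjects must be withdrawn from the study for the following reasons", and one item is "In case of lung transplantation". The same section then says that, for all children who stop study drug for reasons other than withdrawal of consent, "study visits will take place as planned to collect potential study outcomes and AEs". SAP 4.2 repeats this and adds: "The analysis will be performed independently of the fact whether a patient had drug intake or not".

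SAP 4.5 takes the observation nearest the target visit when a visit has several. SAP 6.2.2 summarises efficacy as change from baseline to end of treatment (week 24) in the safety set. Its TTCW definition counts lung transplantation as an event, alongside death.

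**The concern.** The plan regards lung transplantation as a failure in two places: it is a reason for withdrawal and a clinical-worsening event. In the walk-distance and functional-class summaries it has no status. A post-transplant value at Visit 9 is observed, so no missing-data rule reaches it, and nothing in either document censors, replaces or flags it. The value then describes transplanted lungs, yet it is tabulated as change on riociguat.

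The study has one arm and may have few more than 20 children, so nothing offsets such a value and one child can move a mean noticeably. The age-cohort summaries planned in SAP 4.5 are more exposed still, because protocol 4.1 allows a cohort of 5.

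**Working it through.** **No plan figure to reproduce.** The analysis is descriptive, and protocol 7.5 states that the sample size does not come from a formal calculation. The check is therefore a trace of the rules, followed by an illustration.

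**Trace for a child transplanted before week 24**
1. Protocol 8.9: the child meets a listed withdrawal reason, in the section on stopping study medication.
2. If visits continue (protocol 8.9, SAP 4.2), Visit 9 is held. SAP 4.2 keeps its data regardless of drug intake, and SAP 4.5 makes it the week-24 value.
3. If the child instead leaves the study, protocol 6.1.3 and SAP 4.2 require an end-of-treatment visit with the Visit 9 procedures except the x-ray. SAP 4.3 says: "Last visit is defined as last observed value post-baseline (including unscheduled visits, but not including follow-up), if not specified otherwise". If that visit falls after the transplant, a post-transplant value becomes the child's last value.
4. SAP 4.3: no death, so neither 0 m nor class IV is assigned.
5. SAP 6.2.2: the child is an event in TTCW.

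Steps 2 and 3 reach the same result by different routes, provided that an assessment takes place after the transplant.

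**Illustration for mean 6MWD change**

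Inputs:
- N = 20, the minimum number of ERA-treated children in protocol 7.5, used here as the total.
- Baseline b = 300 to 500 m and observed change d = -50 to +150 m. Both are assumptions; the documents give neither.

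Formulas for one child's contribution to the mean:
- as written: d/N
- under the death rule (0 m): -b/N
- gap between the rules: (b + d)/N

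| b (m) | d (m) | d/20 | -b/20 | (b + d)/20 |
|---|---|---|---|---|
| 300 | -50 | -2.5 | -15 | 12.5 |
| 400 | 0 | 0 | -20 | 20 |
| 400 | +100 | +5 | -20 | 25 |
| 500 | +150 | +7.5 | -25 | 32.5 |

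The gap does not need an improvement after transplant: with d = 0 and b = 400 m it is still 20 m. With more than 20 children it shrinks in proportion. In a cohort of 5, with b = 400 m and d = +100 m, it is (400 + 100)/5 = 100 m.

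**WHO class.** One child is 1/20 = 5% of the frequency table, or 1/5 = 20% in a minimum cohort.

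**The case against.** The strongest reply is that SAP 4.2 makes a deliberate and recognised choice: analyse what is observed, on drug or off. Preferring a worst value would then be a matter of taste for an exploratory endpoint, and assigning 0 m to a living child who walked is artificial. This has some force. But the SAP has already left that strategy for death, and it applies the death rule even when the death occurs in follow-up after early termination, when a walk may already be on record from the end-of-treatment visit. Transplantation also differs from merely stopping drug, since it replaces the diseased organ. A sponsor who prefers observed values can defend that, but should say so for this event.

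Several further points stand and limit the concern:
- **Direction.** A reader might infer that a transplanted child would be scored as improved. The documents contain no post-transplant values, and a child assessed within 24 weeks of baseline would be recovering from major surgery. The range above includes a loss.
- **Scope of the contrast with death.** It applies to 6MWD and WHO class only. For echocardiography, NT-proBNP/BNP and quality of life, death has no rule either.
- **Attendance.** The withdrawal header and the continued-visits sentence in protocol 8.9 pull apart, so attendance at Visit 9 is not assured.
- **Visibility.** The transplant appears in TTCW, in the cases sent to the DMC and in the dropout reasons. SAP 4.1 also reports medians and quartiles, which one child in 20 moves little.
- **Likelihood.** WHO class IV and decompensated right heart failure are excluded at entry.

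A reader might also want values after Pott's anastomosis or atrioseptostomy removed. The documents do not support that. Neither procedure is on the withdrawal list, so those children may still be taking riociguat, and dropping children who worsened could flatter the remaining means.

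**Conclusion.** The gap in the rules is real and narrow. For 6MWD and WHO class, the plan treats death as the worst outcome but takes lung transplantation at its measured value, while TTCW counts both as events. For the other efficacy variables it says nothing about values after transplant.

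On the stated assumptions, one such child among 20 adds -2.5 to +7.5 m to the mean 6MWD change as written, and -15 to -25 m under the death rule. It is tempting to set the 12.5 to 32.5 m gap beside the 30 m mean gain of the adult pivotal study (protocol 1.2) and call it bias of that size. That is not supported: the gap compares two conventions, and most of it comes from assigning 0 m.

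The effect depends on a transplant occurring before week 24 with a later assessment, and it touches only exploratory secondary endpoints. The primary objectives of safety, tolerability and pharmacokinetics are not affected. This is a cheap improvement of modest weight. It is best settled in advance, because in an open-label study a rule chosen at the validity review would be chosen with the data in view.

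**What to change.** - **SAP 4.3, 6MWD and WHO class.** Extend the existing rule (6MWD = 0, WHO class = IV) to lung transplantation before week 24, and say that it replaces any value measured after the transplant. Footnote each table with the number of values that come from death and the number from transplantation; this also separates them from living children in class IV.
- **SAP 6.2.2, echocardiography, NT-proBNP/BNP and quality of life.** Flag and list values measured after lung transplantation. Show the change tables with and without them, stating the number of children.
- **Pott's anastomosis and atrioseptostomy.** Keep values after these procedures in the tables and flag them in the listings only.
- **Protocol 8.9.** Reconcile the withdrawal header with the sentence on continued visits, so that it is clear which assessments are expected after a transplant.

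The cost is a few lines of SAP wording, one derivation rule, one flag and a clarification in the protocol. The downside is that the mean 6MWD change and the class distribution become less favourable if such an event occurs.

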The structure of analyses datasets and layout of analysis data displays will follow Bayer standards in the following order of priority: Riociguat Global Standards, Global Medical Standards, and Global Standards for Data Display. Study-specific specifications may be added if required and not covered by the Global Standards.

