4.5 Data Rules

Unless otherwise specified, baseline is the last available non-missing value prior and up to the time of the first intake of study medication, i.e. first dose of riociguat. Change from baseline is calculated as the value at the post-baseline time point minus the baseline value, i.e. value at time point – value at baseline.

Post-treatment values will be considered treatment-emergent if they start within 2 calendar days after the last day of study drug administration, i.e. the treatment-emergent window will be 2 days.

All data from the electronic case report form (eCRF) will be organized and analyzed according to the scheduled visits. Any additional or unscheduled measurements will be included in the listings according to the date/time of assessment. In the case of multiple observations at a specific visit, the observation that is closest to the target visit will be used in the analyses. If observations have the same distance (before and after) to the target visit, the latest one will be used. If the repeated measurements are all taken on the same day, then the last measurement will be used.

Subgroup analyses will be performed by age cohort (≥ 6 to < 12 years and ≥ 12 to < 18 years) and by concomitant PAH medication (ERA only, ERA + PCA, PCA only) specified at Screening. The patients are assigned to the concomitant PAH medication groups specified before date of treatment according to Standardised Drug Grouping (SDG)/Bayer Drug Groupings (BDG), section 6.1.6. Patient’s assignment to PAH medication grouping is depicted in Table 4–1:

Table 4–1: Concomitant PAH medication grouping

Group	SDG (BDG)	
	Endothelin receptor antagonists	Prostacyclins (including analogues and receptor agonists)
ERA only	Yes	No
ERA + PCA	Yes	Yes
PCA only	No	Yes

Listings will be sorted by subject identifier, visit (if applicable), date and time.

Dates will be formatted as DDMMYYYY. Partial dates will be presented on data listings with dashes for the missing parts, e.g. like --MMYYYY. Listing should only present the collected dates, not imputed dates.

Rounding for all variables will occur only as the last step, immediately prior to presentation in listings and tables. No intermediate rounding will be performed on derived variables. The standard rounding practice of rounding numbers ending in 0-4 down and numbers ending 5-9 up will be employed.

Every table, listing and figure will be produced with an electronic date stamp to document when it was produced.

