6.4.1 Adverse event

Adverse events are considered to be treatment-emergent adverse events (TEAE) if they have started or worsened after first application of study drug up to 2 days after end of treatment with study drug.

The safety evaluation of AE data will include:

- Overall summary of AEs
- Overall summary of TEAEs
- TEAEs and by SOC and PT (overall, serious, study drug related, study drug related serious, of special interest, not related to study drug, TEAEs resulting in discontinuation of study drug, study drug related resulting in discontinuation)
- TEAEs by SOC and PT and by maximum intensity (overall, serious, study drug related, study drug related serious, TEAEs of special interest, TEAEs resulting in discontinuation of study drug)
- TEAEs by SOC and PT and by worst outcome (overall, serious, study drug related, study drug related serious, TEAEs of special interest, TEAEs resulting in discontinuation of study drug)
- Common ($\geq 5\%$) TEAEs by PT, common ($\geq 5\%$) serious TEAEs by PT, common ($\geq 5\%$) study drug related TEAEs by PT
- Listings of serious TEAEs, serious TEAEs with outcome of death, serious TEAEs leading to discontinuation of study drug, TEAEs of special interest, TEAEs of special interest leading to discontinuation of study drug, TEAEs leading to discontinuation of study drug and deaths.

Adverse events of special interest are: Hemoptysis, Hypotension and Skeletal related events.

For each SOC and PT, summaries will be made with respect to the proportion of subjects having at least one occurrence of that event in dosing group (0.5 mg, 1.0 mg, 1.5 mg, 2.0 mg, 2.5 mg TID) and overall during the study.

All adverse event tables will be presented overall (all ages). In addition, presentation will be done by age group and concomitant PAH medications for overall summary tables and Common ($\geq 5\%$) TEAEs by PT, common ($\geq 5\%$) serious TEAEs by PT, common ($\geq 5\%$) study drug related TEAEs by PT tables.

Non-TEAEs will be listed only.

Following outputs are part of the DMC package:

- Overall summary of TEAEs
- TEAEs by SOC and PT
- Serious TEAEs by SOC and PT
- Study drug-related TEAEs by SOC and PT
- Serious study drug-related TEAEs by SOC and PT
- TEAEs of special safety interest by SOC and PT
- Listings of deaths
- Listings of all AEs with information of serious adverse events (SAEs), AEs leading to discontinuation of study drug and AEs of special interest.

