In addition all adverse events terms and investigator terms are tabulated.

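### The partial-date rule in SAP 4.3 has no first-dose exception, so on-treatment adverse events dated only to the month or year of first dose drop out of the TEAE tables

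*SAP*

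**What the plan says.** SAP 4.3 explains that tables do not need complete dates, but that adverse events and concomitant medications must be assigned to a phase (pre, during or post). For partial onset dates the rule is: "The 'minimum' rule will be used for start dates which is first day of month or 1st of January". End dates go to the last day of the month or 31 December. Just before this, 4.3 says: "Treatment emergent events, phases, period and relative days will be derived according to standard guidelines". Those guidelines are neither reproduced nor listed among the SAP references. SAP 4.1 orders the sponsor's standards as "Riociguat Global Standards, Global Medical Standards, and Global Standards for Data Display", but for dataset structure and display layout.

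SAP 6.4.1 and protocol 7.4.1 define a TEAE as an event that started or worsened after first dose, up to 2 days after the end of treatment. SAP 4.5 also keys the post-treatment window to onset: "Post-treatment values will be considered treatment-emergent if they start within 2 calendar days after the last day of study drug administration". For everything else, SAP 6.4.1 says: "Non-TEAEs will be listed only".

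**The concern.** The minimum rule pushes an uncertain onset to the earliest possible date. For an event in the month or year of first dose, that date nearly always precedes first dose. A new on-treatment event is then treated as a screening event. It disappears from the TEAE tables by system organ class and preferred term, and from the TEAE-restricted listings: "Listings of serious TEAEs, serious TEAEs with outcome of death, serious TEAEs leading to discontinuation of study drug", and those for events of special interest.

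Protocol 6.2 names TEAE incidence as a primary safety outcome. The events at risk include those around first dose and early titration, and the error runs only towards fewer TEAEs. SAP 6.4.1 also breaks the results down: "presentation will be done by age group and concomitant PAH medications for overall summary tables". In groups that small, one child shows. Nor does the event reappear in a pre-treatment incidence table: protocol 7.4.1 asks for one, but the SAP only lists non-TEAEs.

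The rule also fits poorly with protocol 8.1.1, under which an adverse event record means onset or deterioration after consent. Screening opens at most 2 weeks before Visit 1 (protocol 6.1), so some imputed onsets would precede consent, where the condition would have been medical history.

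**Working it through.** **Example.** First dose on 15 March 2018.

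- Onset known as March 2018: imputed 1 March, pre-treatment.
- Onset known as 2018: imputed 1 January, pre-treatment.
- Onset known as April 2018: imputed 1 April, TEAE (correct).

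The problem is therefore confined to the month of first dose (day missing) or the year of first dose (day and month missing). In a 365-day year the imputed date precedes first dose for 365 − 12 = 353 first-dose dates (day missing) and 365 − 1 = 364 (year only). The exceptions are first doses on the 1st of a month or on 1 January.

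**Inputs.** Treatment lasts 24 weeks = 168 days (protocol 5.3). Consent is at most 14 days before first dose (protocol 6.1). The plan gives no figure for partial dates, so all shares below are conditional on an event having one. Assumptions: first-dose day *d* uniform over the month or year, onset uniform over the 168 days.

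**Share of on-treatment events lost.**

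- Day missing, 30-day month: on-treatment days in the first-dose month are Σ(31 − d) over d = 1..30 = 465. The 30 days for d = 1 are classed correctly, leaving 435. (435/30)/168 = 0.086.
- Year only: Σ min(168, 366 − d) over d = 2..365 = 197 × 168 + 14,028 = 47,124. 47,124/(365 × 168) = 0.768.

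**Of those lost, share imputed before the earliest possible consent** (first dose minus 14 days, so d ≥ 16).

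- Day missing: Σ(31 − d) over d = 16..30 = 120; 120/435 = 0.276.
- Year only: (183 × 168 + 14,028)/47,124 = 44,772/47,124 = 0.950.

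Using every actual start date in 2016–2019 instead gives 0.088, 0.769, 0.284 and 0.950.

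**Effect of one child on an incidence.** 100/20 = 5 points for the 20 ERA-treated children that protocol 4.1 requires as a minimum; 100/10 = 10 points in a cohort of 10 (an even split of 20); 100/5 = 20 points at the planned minimum of 5 per cohort. Each applies only if that child has no other TEAE in the same row.

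**With a floor at first dose,** enumeration over all first-dose dates in a year and all days of the treatment-emergent window leaves no on-treatment event classed as pre-treatment.

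**The case against.** The strongest reply is that the SAP delegates treatment emergence and phase to guidelines that cannot be seen here, and these may already contain the exception. That stands as a condition on the conclusion. It does not settle the matter: the next lines of 4.3 print an explicit rule for the same purpose, and a programmer would reasonably follow it.

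A second reply is that an early start combined with a late end widens the event's interval, so that phase by overlap with treatment would give *during*. But 4.5 and 6.4.1 define treatment emergence by onset or worsening, not overlap.

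Third, few records should be affected. Adverse events are checked every 2 weeks in titration, protocol 8.5 asks for start and stop dates, and serious events are reported within 24 hours of awareness (protocol 8.6). This stands and limits the size, not the direction. The Validity Review Meeting could also catch cases, but no rule tells it what to do.

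Fourth, events do not vanish. They remain in the overall summary of adverse events and in the all-event listings, including the DMC's, and "In addition all adverse events terms and investigator terms are tabulated". An event recorded as worsening on treatment can still qualify. All true, but the TEAE incidences would still be too low.

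Finally, a floor at first dose creates false TEAEs. That is so; the cost is set out with the proposed change.

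**Conclusion.** The concern holds. Followed as written, SAP 4.3 classes new on-treatment events with a partial onset date in the month or year of first dose as pre-treatment, and so lowers a primary safety outcome. The loss is about 9% of day-missing and 77% of year-only on-treatment events, given a partial date and uniform first-dose day and onset. Year-only dates should be rare, so the absolute number is probably small, but it cannot be computed from the documents. The study is descriptive and no test depends on this. The conclusion rests on the standard guidelines not overriding the printed rule. The sponsor should correct or clarify it before database lock.

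**What to change.** Add to SAP 4.3, for adverse events only:

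> If the known part of the start date equals the month (or, for a year-only date, the year) of first dose, and the event is ongoing or its end date, after the maximum rule if partial, is not before first dose, set the start to the later of the minimum-rule date and the first-dose date. Otherwise use the minimum rule. Then apply the usual treatment-emergent window, treating an event imputed to the first-dose date as after first dose.

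Also state what is done with a wholly missing start date, for which 4.3 gives no rule. Footnote the number of TEAEs resting on an imputed start, including in the by-dose tables, where the dose at onset is unknown and the rule would place such events at the starting dose. Leave concomitant medication unchanged. If the standard guidelines already contain such a rule, quoting it in 4.3 is enough.

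The work is one rule, one derivation and one footnote count. The statistical cost is some over-counting, on the same uniform assumptions:

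- Events from the 14 days before first dose, unless an end date excludes them: day missing, Σ min(d − 1, 14)/(30 × 14) = 315/420 = 75%; year only, 5,005/5,110 = 98%.
- Year-only follow-up events of completers not entering the extension (days 171–228, 58 days): those falling in the year of first dose, 9,657/(365 × 58) = 9,657/21,170 = 46%. Day-missing follow-up events of completers are not affected.

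Over-counting is the conservative error for a safety analysis, and the footnote makes it visible.
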